 - (b) Ultrasound: Time from transducer contact on skin to needleout
 - (c) Number of needle sticks/muscle and needle redirection with muscle for E-stim and US
- (2) Weakness after the procedure in targeted and adjoining muscles
- (3) Side effect incidence with each technique
- (4) Patient self-reported satisfaction with each procedure
- (5) Physician global impression of change
- (6) For dystonia, physician rated “Arm Dystonia Disability Scale”
- (7) For spasticity, physician rated Modified Ashworth Scale in targeted and adjoining muscles
- (8) Patient discomfort assessed on a visual analog scale

e) Procedures Involved in the Human Research

Visit 1 - Screening

At the time of the first visit, the protocol, procedures, and the entire consent document will be discussed with the subjects. If the subjects agree to participate, they will sign the consent form and a copy provided before any screening procedures are initiated. Eligibility will be determined by history and physical examination.

The subjects’ history is reviewed and eligibility established. After signing the consent document, the subjects undergo a standard neurologic evaluation focusing on the dystonia and /or spasticity manifestations. Before each treatment visit, women will be given a urine pregnancy test to confirm they are not pregnant.

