Repeated measures ANOVA will be used for the primary outcome. Patients who do not complete all 4 visits will be replaced, and all subjects will be included in the safety analysis. We will use $p < 0.05$ as significance threshold. No interim analysis is planned.

Power analysis

Calculations are based on a α of 5% and a β of 80%, and the published SD for ona-BoNT-A therapy of 20%. There is an expected variation of 15% for the procedure. We hypothesize that US will demonstrate non-inferiority in comparison to E-stim based on previous experience performing the procedures. A total of 18 subjects (9 from each site) are needed to show the desired 15% variation. 15 subjects will be enrolled at each site to allow for screen failures and dropouts.

h) Provisions to Monitor the Data to Ensure the Safety of subjects

Adverse events will be reviewed at every visit. Patients will be asked specifically about pain or weakness. Patients will also have the option to contact the investigators between scheduled visits to report unanticipated events.

The procedures will be stopped if an individual reports any unexpected adverse event NCI grade 3 or higher.

Serious or unexpected adverse events and other unanticipated problems will be reported orally as soon as possible and in writing within 7 days if life-threatening and within 15 days otherwise. Expected or non-serious adverse events will be reported at the time of continuing review. Adverse events will be reviewed at every visit. Patients will be asked specifically about pain or weakness. Patients will also have the option to contact the investigators between scheduled visits to report unanticipated events.

The procedures will be stopped if an individual reports any unexpected adverse event NCI grade 3 or higher.

Serious or unexpected adverse events and other unanticipated problems will be reported orally as soon as possible and in writing within 7 days if life-threatening and within 15 days otherwise. Expected or non-serious adverse events will be reported at the time of continuing review.

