- 3) Accumulated safety and data information will be reviewed by the monitors during the monthly study team calls.
- 4) The study does not require any stopping rules for interrupting the study or altering the study design. The treatments are standard of care.
- 5) Onabotulinumtoxin A is not under study. The subjects will receive their standard clinical treatment.
- 6) AEs will be classified as mild, moderate or severe based upon the following criteria: Mild = symptoms do not alter the subject’s normal functioning, Moderate= symptoms produced some degree of impairment to function but are not dangerous, uncomfortable or embarrassing to the subject, Severe = symptoms are dangerous to the subject’s well-being and causes significant impairment of function or incapacitation.

The relationship of the AE to the treatment will be classified as follows:
Related: there is good reason(s) and sufficient evidence to assume that there is a causal relationship with the treatment and the AE. Not related: there is good reason(s) and sufficient evidence to exclude a causal relationship with the treatment.

All AEs will require the investigator to obtain adequate information to determine the outcome of the AE and to assess whether it meets criteria as a serious adverse event (SAE), which requires immediate notification to the funding agency and ethics review board. The investigator will obtain sufficient information to determine the causality of the AE (i.e. treatment or

other cause); and provide their opinion on causal association (i.e., whether they consider the AE related or not related to the study intervention). Subjects will receive follow up until the AE either resolves completely or stabilizes to a level acceptable to the investigator.

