All SAEs will be reported within 24 hours of the investigator's knowledge of the event to the ethics review board and/or funding agency. An SAE is any AE during the time period of the study that: 1) results in death, 2) is life threatening and places the subject at immediate risk of death, 3) results in in-patient hospitalization, 4) results in significant disability/incapacity, where the disability is a substantial disruption of a person's ability to conduct normal daily life functions, 5) is an important medical event that may not result in death, be life threatening, or require inpatient hospitalization, but which based upon the appropriate medical judgment may require medical and/or surgical intervention to prevent one of the outcomes listed above.

- 7) All data will be reviewed by Drs. [name] and [name] for completeness and accuracy
- 8) Should a temporary or permanent suspension of the study occur, in addition to the PPHS, we would need to inform the funding agency and the NIH.

j) Withdrawal of Subjects

Participants may withdraw from the study at any time, with an early withdrawal, a follow-up visit to examine and ensure patient safety. Withdrawal or discontinuation due to an AE will be distinguished from withdrawal/discontinuation due to an insufficient response to the study treatment. It is rare that the study team will request a subject be withdrawn from the study because the treatment is standard of care, but if an adverse event does occur requiring the subject be withdrawn, a follow up visit to examine and ensure patient safety will be performed.

6) Risks to Subjects

The risks of BoNT injection will be reviewed with patients again at time of enrollment in this protocol. The possible side effects are:

- Over relaxation or muscle weakness of the targeted muscles. Furthermore, non-targeted muscles may be affected.
- Participants may experience pain and discomfort while receiving the injections.
- Infection at the injection site.
- A possibility the muscles will not be targeted similar to your previous treatments and you may not experience the same results as previous clinical treatments.

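### The adverse event severity definitions are not exhaustive, so some expected events cannot be graded as written; side-effect incidence by technique is unaffected

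*Combined protocol and SAP*

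**What the plan says.** The three grades are in item 6 of the numbered safety-monitoring list that precedes section 5 j) (Withdrawal of Subjects). The rule covers adverse events generally: "AEs will be classified as mild, moderate or severe based upon the following criteria". The definitions are:

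- The lowest grade reads: "Mild = symptoms do not alter the subject’s normal functioning".
- For the middle grade the text is: "Moderate= symptoms produced some degree of impairment to function but are not dangerous, uncomfortable or embarrassing to the subject".
- The top grade applies when "symptoms are dangerous to the subject’s well-being and causes significant impairment of function or incapacitation".

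Section 5 h) instructs staff, for every visit: "Patients will be asked specifically about pain or weakness". Section 6 (Risks to Subjects) lists weakness of targeted and non-targeted muscles, and states: "Participants may experience pain and discomfort while receiving the injections". The same section 5 h) ties a stopping provision to NCI grade 3 and above for unexpected events. It does not say how NCI grades map to the three levels of item 6.

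The corresponding item under Study Endpoints, secondary outcome (3), is "Side effect incidence with each technique".

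**The concern.** The grades mix three ideas: effect on function, danger, and whether the subject is bothered. Mild is defined by function alone. Moderate adds three exclusions: danger, discomfort and embarrassment. Severe requires danger and significant impairment together. Nothing in the text says what to do when an event meets none of the three definitions.

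A sore or weak hand that the patient finds uncomfortable and cannot use normally, without any danger, is an ordinary event after this procedure. It is not mild, because function has changed. It is excluded from moderate, because it is uncomfortable. It is not severe, because it is not dangerous. The rater must then break one of the definitions or leave the grade blank. At stake is the consistency of the severity field, and of any later description of events by severity. Two sites contribute data without a coordinating center (section 15), and section 5 g) leaves quality control to each site's usual practice.

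**Working it through.** The plan gives no figure to reproduce, so the check is whether the definitions cover every case.

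**Inputs.** All three definitions come from item 6. They use four attributes: impairment (none, some, significant), dangerous (no, yes), uncomfortable (no, yes) and embarrassing (no, yes). That gives 3 × 2 × 2 × 2 = 24 profiles.

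**Rules as written.**
- Mild: impairment is none.
- Moderate: impairment is present, and the event is not dangerous, not uncomfortable and not embarrassing. I read some degree of impairment generously, so that it includes significant impairment.
- Severe: dangerous, and impairment is significant.

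Each row below covers the four combinations of uncomfortable and embarrassing.

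| Impairment | Dangerous | Profiles | Mild | Moderate | Severe | No grade |
|---|---|---|---|---|---|---|
| none | no | 4 | 4 | 0 | 0 | 0 |
| none | yes | 4 | 4 | 0 | 0 | 0 |
| some | no | 4 | 0 | 1 | 0 | 3 |
| some | yes | 4 | 0 | 0 | 0 | 4 |
| significant | no | 4 | 0 | 1 | 0 | 3 |
| significant | yes | 4 | 0 | 0 | 4 | 0 |
| Total | | 24 | 8 | 2 | 4 | 10 |

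**Three faults follow.**
1. Non-dangerous, impairing, and uncomfortable or embarrassing: 3 + 3 = 6 profiles with no grade. All 4 profiles that are non-dangerous, impairing and uncomfortable are among them.
2. Dangerous with some but not significant impairment: 4 profiles with no grade.
3. Dangerous with no impairment: 4 profiles graded mild.

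**Sensitivity to the reading.**
- If moderate excludes significant impairment, the one non-dangerous, significant profile now graded moderate also loses its grade: 10 + 1 = 11 of 24.
- If danger or significant impairment alone were enough for severe, 3 profiles would still have no grade (some impairment, not dangerous, uncomfortable or embarrassing). The 4 dangerous profiles without impairment would then be both mild and severe.

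**Effect of the smallest edit.** If discomfort and embarrassment no longer exclude an event from moderate, moderate covers 8 profiles and the total graded is 8 + 8 + 4 = 20. The 4 left are the dangerous events with some impairment. Deleting the exclusion alone is therefore not enough.

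**What needs the grade.** A count of side effects per technique uses none of these labels and does not change under any of these readings.

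**The case against.** The strongest reply is that little depends on this scale. The listed outcome is incidence, and the analysis text in section 5 g) describes no analysis by severity. Procedural discomfort is a separate secondary outcome on a visual analog scale (Appendix 1, visits 1 and 3). Weakness is also a separate outcome, measured by visual analog scale, MRC scale and force transducer (section 5 e), Visit 2). Serious events have their own criteria and a 24-hour reporting rule, and the stopping provision uses NCI grade. All of this stands, and it limits the consequence.

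A reader might go further and infer that the comparison of side effects between techniques fails, or is biased because section 6 attributes discomfort to the stimulation current. The documents do not support that: no severity-by-technique comparison is planned in the text, and incidence can be counted without a grade. A reader might also infer that pain and weakness as a whole cannot be graded. That is too broad. Pain that leaves functioning unchanged is mild, and impairing weakness that is neither dangerous, uncomfortable nor embarrassing is moderate. Divergence between the sites is a possibility, not something the documents show; item 6 states one scale, and safety data are reviewed on monthly calls.

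It can also be said that moderate was meant as not dangerous but possibly uncomfortable or embarrassing. That may be the intent, but the sentence says otherwise. Even that reading leaves the 4 dangerous profiles with some impairment without a grade.

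**Conclusion.** The point holds as a classification rule that fails as written. Item 6 requires a grade for every adverse event, yet its definitions leave 10 of 24 logical profiles without one and label 4 dangerous profiles mild. The affected profiles include events that the protocol lists as risks and tells staff to ask about, when those events impair function and bother the subject. The scale is also unconnected to the NCI grading in section 5 h).

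The size is modest. The defect reaches the severity field and any description built on it. It does not reach side-effect incidence by technique, the discomfort and weakness outcomes, or serious event reporting. The number of events affected cannot be derived from the documents, and 10 of 24 must not be read as a proportion of events.

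The conclusion rests on the literal wording, and on the assumption that no tie-breaking rule stands in the part of the safety-monitoring list before item 3, which was not in the text available to me.

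**What to change.** Reword item 6 so that the three grades are exhaustive and mutually exclusive. Remove discomfort and embarrassment as exclusions from moderate. Close the gap between moderate and severe, and state explicitly where dangerous events with no impairment or only some impairment belong; that assignment is for the investigators to make. The new wording can be tested on the 24 profiles above: each should receive exactly one grade.

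Print the same definitions on the adverse event form at both sites. Reconcile the three-level scale with the NCI grading in section 5 h), so that it is clear which scale serves which purpose and how the two are recorded for the same event.

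The cost is wording in item 6 and on the adverse event form. No outcome, sample size or treatment procedure changes.

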At the NIH site, patients will be introduced to the research project from the BoNT clinic, including the neurology and movement disorders practitioners at Suburban Hospital, Holy Cross Hospital, George Washington University Medical Center, Georgetown University Hospital, Johns Hopkins University Medical Center, The Parkinson Disease and Movement Disorders Center of Maryland, University of Maryland and others.

Subjects potentially interested will be provided information about the study, copy of the consent form will be provided which subjects can review and bring home for family or friends to review. They will have the opportunity to contact the investigators at the Icahn School of Medicine or the NIH for questions. We anticipate recruiting a total of 30 subjects with 15 subjects at each site within one year.

b) Inclusion and Exclusion Criteria

Inclusion criteria

- Confirmed diagnosis of focal upper extremity dystonia (FHD) or upper limb spasticity
- Stable onabotulinumtoxinA dose regimen with a stable response as judged by the physician and patient for at least 2 treatment sessions.
- Age 18 and above

Exclusion criteria

- Contraindications to botulinum toxin
- Pregnancy or nursing
- Cognitive impairment that prevents reliable outcome measures of self-report

[figure not shown]
c) Number of Subjects

The study will enroll a total of 30 patients, with 15 patients at each site. Target number of patients to be treated and complete the study will be 18 subjects (to have sufficient statistical power).

d) Study Timelines

This is a randomized cross-over study, with two study sites. 4 outpatient visits of approximately 30-60 minutes each will take place over 16- 24 weeks. All NIH patients will also be enrolled in protocol 85-N-0195, and botulinum injections will be done under that protocol.

An outline of the procedures is depicted in the figure below:

The study anticipates enrollment of the first subject in February 2015. The study team anticipates an enrollment period of approximately 36 months with the last patient to be enrolled Dec. 2020 with the primary analysis completed by June 2021.

Study Endpoints

Outcome measures

Primary outcome measures

Improvement in dystonia or spasticity severity on a physician and patient self-reported visual analog scale.

Secondary outcome measures

- (1) Duration of the injection procedure as follows:
 - (a) E-Stim: time from needle In to needle Out

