The subjects return to the clinic one month after injection, at the anticipated peak effect of ona-BoNT-A therapy. They will complete self-rating forms (Patient Global Impression of Change and Visual Analog scale for pain) and be evaluated by a blinded rater, who will not know what injection technique has been used (the patients will be instructed to withhold that information). The evaluation will include: visual analog benefit scale; visual analog weakness scale; review of side-effects; standardized clinical scale assessment (by clinician): Arm Dystonia Disability Scale for limb dystonia; Ashworth scale for spasticity; Global Assessment of Change/Clinical Global Impression of change; weakness assessed on the MRC scale; weakness of targeted and neighboring muscles as assessed with a mechanical force transducer (standard for both sites).

The blinded rater is the non-injecting neurologist who will be one of the co-investigators who did not participate in the subject's study visit and will remain the blinded rater consistently for the subject for the study. The blinded rater will provide an assessment of dystonia or spasticity without know the muscle targeting method used. The visual analog scales will be used by the blinded rater but the patient will complete a satisfaction scale of the procedure on a 10 point scale (see the attached appendix 1)

Visit 3:

An interval history will be obtained, and a targeted examination repeated. If on re-evaluation the patient's dystonia or spasticity has increased and retreatment is deemed to be clinically indicated then the patient will be re-injected. The muscle pattern and dose will remain the same as on visit one. Muscle localization will be with the second technique (crossover). As in Visit 1, the process of completing the injection of the subject will be videotaped. If on clinical evaluation the patient's severity of the patient's dystonia or spasticity does not require treatment re-injection will be deferred. The patient will return when clinically symptomatic (16-24 weeks), re-evaluated and re-injection will occur when clinically appropriate, as described above.

Visit 4:

This will be identical to visit 2, i.e. 4 weeks post re-injection. The study ends after visit 4.

End of Participation

Subjects will be referred back to their clinical care. If any new information pertaining to the patients' care is obtained during the study, it will be shared with the patients and their healthcare providers.

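### Patients who withdraw after an injection but before its 4-week rating have no planned outcome score for that technique, although a withdrawal visit is held, and they are then replaced

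*Combined protocol and SAP*

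**What the plan says.** All references are to the combined protocol and SAP.

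- **Section 5j, Withdrawal of Subjects.** "Participants may withdraw from the study at any time, with an early withdrawal, a follow-up visit to examine and ensure patient safety". No visual analog scale (VAS), clinical scale, rater or timing is named for this visit. The section then separates two reasons for leaving: "Withdrawal or discontinuation due to an AE will be distinguished from withdrawal/discontinuation due to an insufficient response to the study treatment".
- **Section 5d, Study Endpoints.** The primary outcome is "Improvement in dystonia or spasticity severity on a physician and patient self-reported visual analog scale".
- **Section 5e, Visits 2 and 4.** On the timing of the first rating: "The subjects return to the clinic one month after injection, at the anticipated peak effect of ona-BoNT-A therapy". Visit 4 repeats this 4 weeks after the second injection. No other visit collects the benefit VAS or the blinded ratings of response.
- **Section 5g, Analysis of data.** The primary outcome is analysed by repeated measures ANOVA. "Patients who do not complete all 4 visits will be replaced, and all subjects will be included in the safety analysis". No method for missing data is given.
- **Section 5c.** The trial enrols 30. "Target number of patients to be treated and complete the study will be 18 subjects".
- **Hypotheses.** Section 1 expects no significant difference between the techniques. The power analysis expects ultrasound to be non-inferior to electrical stimulation.

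**The concern.** Each period consists of one injection and one rating. Once the injection is given, the treatment for that period is complete and its result can still be observed, even if the patient wishes to leave. The plan names poor response as a reason for leaving and arranges a visit for those who leave, yet schedules no outcome rating at that visit. The missing score may then be missing because of the very thing the trial measures.

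The replacement rule makes this worse. The patient's place is filled by someone who completes, so the final 18 are selected for not having left. If one technique produces more poor responders, more of its poor results disappear and the two techniques look more alike. A trial that hopes to find similarity should guard against errors in that direction.

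**Working it through.** **Step 1. The plan's own figures.** Enrolment 30 less 18 completers is 12, and 12/30 = 40%. The power analysis describes this allowance as covering screen failures and dropouts together. The 18 can be approximately reproduced as a paired comparison: difference 15, SD of the within-patient difference read as 20, two-sided 5%, 80% power. That gives n = 16 by paired t, with 85% power at 18. The point below does not depend on that reading.

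**Step 2. Which leavers are unscored.**

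| Patient leaves | Rating for the last technique received | What removes the patient |
|---|---|---|
| After Visit 1, before Visit 2 | None planned | No rating, then replacement |
| After Visit 2, before the second injection | Already taken at Visit 2 | Replacement rule only |
| After the Visit 3 injection, before Visit 4 | None planned | No rating, then replacement |

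Only the first and third rows are a gap in data collection.

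**Step 3. Direction and possible size.** The documents give no failure or withdrawal rate, so every input here is an assumption. Let a failure score 40 VAS points below a usual response. Let p be the failure rate with a technique, and w the probability that a failure leaves before rating, the same for both techniques. Failures are independent between techniques.

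- Failure proportion among those rated = p(1 − w) / (1 − pw)
- Observed difference = 40 × (difference of these proportions)
- Patients lost = 1 − (1 − p₁w)(1 − p₂w)

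Example, 10% against 30% with w = 0.5: 40 × (0.15/0.85 − 0.05/0.95) = 40 × (0.1765 − 0.0526) = 4.95. Patients lost: 1 − 0.95 × 0.85 = 19%.

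| Failure rates | True difference | w = 0.1 | w = 0.5 | w = 1 |
|---|---|---|---|---|
| 10% and 30% | 8.0 | 7.5 (4% lost) | 5.0 (19% lost) | 0 (37% lost) |
| 10% and 20% | 4.0 | 3.7 (3% lost) | 2.3 (14.5% lost) | 0 (28% lost) |
| Equal | 0 | 0 | 0 | 0 |

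**Step 4. A second model, for the non-inferiority claim.** Again the inputs are assumptions: mean benefit 50 with electrical stimulation and 35 with ultrasound; SD 20 per period; correlation 0 or 0.5; the 15 treated as a margin, which the protocol does not call it. A patient scoring below 20 (or 30) with either technique leaves with the stated probability. The analysis uses 18 completers only, so this combines the missing rating with the replacement rule. The true difference equals the margin, so the false non-inferiority rate should be 5% (one-sided).

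| Probability of leaving | Patients lost | Completer difference (true −15) | False non-inferiority |
|---|---|---|---|
| 0.25 | 7% to 14% | −14.5 to −14.1 | 6% to 7% |
| 0.5 | 14% to 26% | −13.9 to −12.8 | 8% to 10% |
| 1 | 25% to 50% | −12.3 to −8.0 | 15% to 41% |

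Both models shrink the difference. The effect is slight when few leave and large only when most poor responders leave unrated.

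**The case against.** **Timing.** Visit 2 falls at the expected peak effect, so a patient who finds the response insufficient will often reach that view at or after the rating. A reader might infer that a technique's failures generally go unscored. The documents do not support that: anyone leaving between Visits 2 and 3 has already been rated, and is lost only through the replacement sentence in section 5g. This stands and narrows the point.

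**Analysis is not powerless.** A reader might infer that no analysis could recover these patients. That goes too far. Section 5j requires the reason for leaving to be distinguished, so a prespecified rule could count such a withdrawal as a failure or assign a poor score. No such rule is written, and an assigned score rests on assumption where a rating would not.

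**Numbers at risk.** Patients must have a stable dose and response over at least 2 sessions, and muscles, dose and dilution are unchanged. Section 6 rates the chance of unequal targeting as very low. Early failures may therefore be few. Section 5j also calls withdrawal rare, but only withdrawal requested by the study team. A reader might take the 40% allowance as the size of this loss. It is not, since it includes screen failures who were never injected.

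**The repair.** A rating after the first injection alone makes no within-patient pair, a leaver may decline to attend, and section 5j names no rater. These are fair limits. But a leaver after the second injection does complete a pair. A mixed model can use a single rating, and the missing second score then depends on a score that was observed. Section 5e already keeps one blinded rater with each patient throughout.

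**Silence.** Section 5j does not forbid outcome ratings, and section 5g does not say outright that replaced patients leave the efficacy analysis. Both are inferences. Even so, nothing provides for the ratings, and inclusion of all subjects is promised for safety alone.

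**Conclusion.** The point holds for withdrawals between an injection and its 4-week rating. These patients have no planned score for that technique, although a visit is held and poor response is a foreseen reason for leaving. They are then replaced.

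The bias is toward no difference if poor response is commoner with one technique and poor responders leave equally readily after either. With equal failure rates and equal readiness to leave there is no such bias, only lost precision. If readiness to leave differs, which is possible because patients know their technique, the direction is not assured.

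The size cannot be fixed from the documents. The 10%, 20% and 30% failure rates and the 40-point deficit are illustrations; no figure in the protocol supports them. With few early leavers the effect is under one VAS point in the first model. With only 18 completers, a handful of selective losses could still matter. The change is worth making because it is cheap, but it works only if the replacement rule is amended with it.

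**What to change.** 1. **Section 5j.** Ask a patient who withdraws after an injection to attend the already planned follow-up visit as near as possible to 4 weeks after that injection. Have the patient's assigned blinded rater complete the Visit 2/4 VAS and scales there, with the patient's own forms, unless the patient declines.
2. **Section 5g.** State that replacement serves only to secure the number of completers. State that every rating obtained, including from replaced patients, enters the primary analysis under the technique received. Use a mixed model that accepts incomplete pairs. Flag off-schedule ratings and leave them out in a sensitivity analysis.
3. **Reporting.** Tabulate adverse-event and insufficient-response withdrawals by technique last received.

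The cost is wording in two sections, some rater time at a visit that is already planned, a few off-schedule ratings and slightly more analysis work. Section 11 already provides $75 for extra visits. No treatment or clinical rule changes.
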